Outcome ascertainment will be performed in two ways. First, data elements within the PEDSnet common data model (CDM), which comprises structured data extracted from EHRs will be examined to identify the select medical events of interest. Each event will be defined using algorithms that will include diagnostic codes and if needed procedure and medication codes, recorded in the EHR. Second, because not all symptoms, signs, and health problems are included in the structured data as diagnosis codes, a chart review of the EHRs for all eligible study patients will be conducted to examine unstructured text data not captured in the CDM to identify additional patients with the select medical events of interest.

Patients with status epilepticus diagnostic codes in their record will be identified from the cohort and will have their results presented separately in sub tables. They will also contribute to the main study populations. This is to fulfill commitment to examine outcomes in SE patients when exposed to lacosamide. It is assumed that any patients treated with a loading dose of LCM will be more likely to be in SE and proving refractory to treatment than the usual seizure presentation in children.

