### 5.3.2 Baseline (pre-index) period

The baseline period for this study will be the 3 months prior to either the first newly initiated qualifying treatment episode of a higher IV LCM dose or a recommended initial IV LCM dose; for patients less than 3 months of age at index event, the baseline period will be birth through index event.

Data from the baseline period will be used to determine the indications for LCM and to define a new treatment episode. All available data prior to the index date will be used to evaluate the patient characteristics, diagnosis, procedures, and medications administered, dispensed or prescribed (AEDs, benzodiazepines and non-AEDs) medications, and identify preexisting

conditions of interest, if any. Preexisting medical events of interest are not exclusion criteria in this study; instead, they will be used to characterize the patient population. Section 5.5.6 details pre-existing medical events of interest that will be evaluated during the baseline period.

Potential indications for IV LCM include but are not limited to epilepsy, febrile seizures, and status epilepticus. The indications in both the higher and recommended IV LCM cohorts will be classified as follows:

- Patients with only one of the listed potential indications in the baseline period will be assigned the identified indication
- Patients with none of the listed potential indications in the baseline period will be classified as having other indications
- Patients with more than 1 of the listed potential indications in the baseline period will be classified as having multiple indications.

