#### 5.4.1 Plan for data collection

The PEDSnet database consists of electronic medical records and is not an administrative claims database. It consists of both structured and unstructured data that is recorded by physicians during all health encounters that patients have in the healthcare network.

The study primary outcomes will be ascertained in two steps; i) review of coded events in the common data model (CDM) and ii) medical chart extraction which will include both coded data and free text. PEDSnet uses Systematized Nomenclature of Medicine-Clinical Terms (SNOMED-CT) to represent the diagnoses; SNOMED-CT, ICD-9, ICD-10, CPT-4 and HCPCS codes to map procedures; RxNorm for dispensed and prescribed medications; and LOINC to represent laboratory results observations. The medical charts are considered the gold standard as they contain the original source of information for the medical encounters and include free hand information that is recorded by the physician during a health encounter. Therefore, including the medical chart review in addition to using data from the CDM will ensure that all available clinical information is utilized to validate the database findings and answer any queries.

**First step:** The PEDSnet network uses SNOMED-CT to enable standardization and pooling of diagnoses data across the across the 8 health systems included in the network. Initially, data will be evaluated relating to the study outcomes using the SNOMED-CT codes in the common dataset. The data in the CDM are coded using SNOMED-CT, an international logic-based, controlled vocabulary used in clinical care that enables meaning-based retrieval of clinical information from electronic health records. SNOMED CT is the most comprehensive, multilingual clinical terminology in the world, containing more than 300,000 medical concepts (diagnoses or findings), divided into hierarchies as diverse as body structure, clinical findings, geographic location and pharmaceutical/biological product. Each concept is represented by an individual code number and several concepts can be used simultaneously to describe a complex condition, for example presenting symptoms arising from a disease. This allows for separation of symptoms of drug exposure versus a comorbid chronic condition e.g. cardiac arrhythmia. Consequently, it is expected that the data in the CDM will include detailed information on the study outcomes.

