## **5.5 Variables**

### **5.5.1 Primary outcome measure**

The following primary variables will be measured to meet the study objectives:

- The incidence rate and incidence rate ratio of cardiac disorders (selected preferred terms (PTs) as described in Section 5.5.5)
- The incidence rate and incidence rate ratio of general disorders and administration site conditions (selected PTs as described in Section 5.5.5)
- The incidence rate and incidence rate ratio of injury, poisoning and procedural complications (selected PTs as described in Section 5.5.5)
- The incidence rate and incidence rate ratio of investigations (i.e. the incidence rate of ECG PR prolongation)
- The incidence rate and incidence rate ratio of skin and subcutaneous tissue disorders (selected PTs as described in Section 5.5.5)
- The incidence rate and incidence rate ratio of drug reactions with eosinophilia and systemic symptoms syndrome (selected PTs as described in Section 5.5.5)
- The incidence rate and incidence rate ratio of severe cutaneous adverse reactions (selected PTs as described in Section 5.5.5)
- The incidence rate and incidence rate ratio of hypersensitivity (selected PTs as described in Section 5.5.5)
- The incidence rate and incidence rate ratio of nervous system disorders (selected PTs as described in Section 5.5.5)
- The incidence rate and incidence rate ratio of metabolism and nutrition disorders (selected PTs as described in Section 5.5.5)

- The incidence rate and incidence rate ratio of psychiatric disorders (i.e. abnormal behavior)

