Maculopapular eruption (disorder)	SCTID: 247471006
Vesiculobullous rash (morphologic abnormality)	SCTID: 14912003
Papulovesicular rash (morphologic abnormality)	SCTID: 4538007
Complaining of a rash (finding)	SCTID: 162415008
Application site rash (disorder)	SCTID: 95371007
Cutaneous hypersensitivity (disorder)	SCTID: 21626009
Nervous System disorders	
Dizziness (finding)	SCTID: 404640003
Dizziness present (situation)	SCTID: 162260006
Dizziness of unknown cause (finding)	SCTID: 429530004
Dizziness due to drug (disorder)	SCTID: 473188002
Dizziness on standing up (finding)	SCTID: 407645004
Postural dizziness (finding)	SCTID: 103017008
Dizziness and giddiness (finding)	SCTID: 271789005
Somnolence	
Drowsiness, function (observable entity)	SCTID: 79519003
Drowsy (finding)	SCTID: 271782001
Complaining of somnolence (finding)	SCTID: 272026007
Daytime somnolence (finding)	SCTID: 141000119100
Excessive somnolence (finding)	SCTID: 372947007
Disorders of excessive somnolence (disorder)	SCTID: 194439006
Somnolence syndrome (disorder)	SCTID: 370971007
Paresthesia (finding)	SCTID: 91019004
Paresthesia of upper limb (finding)	SCTID: 95673003
Facial paresthesia (finding)	SCTID: 95665007
Paresthesia of foot (finding)	SCTID: 309087008
Paresthesia of hand (finding)	SCTID: 309086004
Paresthesia of finger (finding)	SCTID: 762374005

Table 3 SNOMED-CT concepts for the study	
Study outcome	SNOMED code
Transient paresthesia (finding)	SCTID: 135873002
Circumoral paresthesia (finding)	SCTID: 1141007
Paresthesia of lower extremity (finding)	SCTID: 429783005
Paresthesia of right upper limb (finding)	SCTID: 15973701000119104
Paresthesia of right lower limb (finding)	SCTID: 15634791000119106
On examination - paresthesia present (finding)	SCTID: 163707002
Injection site paresthesia (disorder)	SCTID: 95399003
Paresthesia of left lower limb (finding)	SCTID: 15634841000119109
Paresthesia of left upper limb (finding)	SCTID: 15973661000119106
Oral paresthesia (disorder)	SCTID: 95524000
Paresthesia of mucous membrane (finding)	SCTID: 95358009
Paresthesia of tongue (disorder)	SCTID: 95527007
Numbness of skin (finding)	SCTID: 102603008
Burning sensation of skin (finding)	SCTID: 762397008
Prickling sensation of skin (finding)	SCTID: 162248005
Numbness and tingling sensation of skin (finding)	SCTID: 101000119102
Finding of sensation of skin (finding)	SCTID: 297971001
Altered sensation of skin (finding)	SCTID: 247325003

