Skin sensation disturbance (finding)	SCTID: 80910005
Complaining of paresthesia (finding)	SCTID: 31048100
Loss of consciousness	
Loss of consciousness (finding)	SCTID: 419045004
Brief loss of consciousness (finding)	SCTID: 32834005
Moderate duration loss of consciousness (finding)	SCTID: 40863000
Prolonged loss of consciousness (finding)	SCTID: 7862002
Syncope	SCTID: 271594007
Syncope and collapse (disorder)	SCTID: 309585006
Metabolism and nutrition disorders	
Appetite disorder	
Non-organic loss of appetite (disorder)	SCTID: 192017004
Appetite problem (finding)	SCTID: 289163007
Appetite symptom (finding)	SCTID: 161824009
Centrally acting appetite suppressant adverse reaction (disorder)	SCTID: 292259006
Altered appetite (finding)	SCTID: 249473004
Eating disorders management (procedure)	SCTID: 386264009
Decrease in appetite (finding)	SCTID: 64379006
Non-organic loss of appetite (disorder)	SCTID: 192017004

Table 3 SNOMED-CT concepts for the study	
Study outcome	SNOMED code
Decreased appetite Decrease in appetite (finding)	SCTID: 64379006
Diet refusal Refusing food (finding) Does not eat (finding) Unable to eat (finding)	SCTID: 105481005 SCTID: 288887001 SCTID: 288885009
Hypophagia Decrease in appetite (finding) Non-organic loss of appetite (disorder)	SCTID: 64379006 SCTID: 192017004
Food aversion Aversion to food or drink (finding) Finding of food aversion and cravings (finding) Sensory aversion to particular foods (finding) Aversion to particular food (finding)	SCTID: 248134002 SCTID: 289143000 SCTID: 16230791000119104 SCTID: 248135001
General disorders and administration site conditions	

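### The primary nervous-system outcome counts loss of consciousness and somnolence whatever their cause; in children treated for seizures this pulls a real dose effect toward 1, and no planned analysis shows the outcome without them.

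*Protocol*

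**What the plan says.** - **Outcome.** Section 5.5.1 lists among the primary measures "The incidence rate and incidence rate ratio of nervous system disorders (selected PTs as described in Section 5.5.5". Section 5.5.5 gives five components: dizziness, somnolence, paresthesias, loss of consciousness and syncope.
- **Codes.** In Table 3, loss of consciousness has four codes, graded only by duration (for example "Prolonged loss of consciousness (finding"). Somnolence has seven (for example "Drowsy (finding"). None names a cause. Dizziness, by contrast, has a cause-specific code, "Dizziness due to drug (disorder", alongside its general ones.
- **Population.** Section 5.3.2: "Potential indications for IV LCM include but are not limited to epilepsy, febrile seizures, and status epilepticus". Section 5.1 adds: "It is assumed that any patients treated with a loading dose of LCM will be more likely to be in SE".
- **Counting.** Section 5.9.1.2 counts a child once per outcome, at the first record after the index date, and time at risk stops there. Section 7.1 defines an adverse event without requiring a link to the drug.
- **Separating drug from disease.** Section 5.4.1 says of SNOMED-CT that several concepts can be combined, and: "This allows for separation of symptoms of drug exposure versus a comorbid chronic condition e.g. cardiac arrhythmia".
- **Pre-existing events.** The lists in sections 5.5.3 and 5.9.1.1 contain no nervous-system item. The exclusion analysis in section 5.9.1.4 relies on pre-existing events of interest.

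**The concern.** Follow-up begins at the index dose and is confined to the inpatient stay (section 5.3.3). That is when a child being treated for seizures is most likely to be ictal, post-ictal or sedated. A record of drowsiness or unconsciousness made then counts in the nervous-system outcome on the same footing as a state caused by the dose.

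Two things follow. Background events of this kind are added to the numerator in both groups, so a true difference between doses looks smaller as a ratio. And because each child counts once for the whole system organ class, an early post-ictal drowsiness record ends that child's time at risk, so a later dizziness event no longer counts in the class-level outcome.

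A rate ratio near 1 in this study could be read as reassurance about loading doses. A reader needs to see how much of that ratio is carried by components that the treated disease can also produce.

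**Working it through.** **No plan figure to reproduce.** The protocol gives no event rates, power or effect size for this outcome. The only count, 875 in section 5.9.3, is a feasibility number before the full criteria. Everything below is illustration on assumed inputs.

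**Inputs (all assumed).**
- Drug-caused nervous-system events: 5% of the comparator group, 10% of the high-dose group (true ratio 2.0).
- Share of children in SE: 45% in both groups, so there is no confounding by SE.
- Disease-caused loss of consciousness or drowsiness recorded after index: b = 5% or 20% of SE children, none in the others.
- Equal follow-up.

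**Formula.** Observed ratio = (0.10 + 0.45b) / (0.05 + 0.45b).

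- b = 5%: (0.10 + 0.0225) / (0.05 + 0.0225) = 0.1225 / 0.0725 = 1.69.
- b = 20%: (0.10 + 0.09) / (0.05 + 0.09) = 0.19 / 0.14 = 1.36.

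**Same result in general form.** If f is the share of comparator events that are disease course, and the same background is present in both groups, the observed ratio for a true 2.0 is f + 2(1 − f) = 2 − f.

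| f | Observed ratio |
|---|---|
| 25% | 1.75 |
| 50% | 1.50 |
| 75% | 1.25 |
| 90% | 1.10 |

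The two cases above correspond to f = 0.0225/0.0725 = 31% and f = 0.09/0.14 = 64%.

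**Masking.** The sums above treat the two kinds of event as never occurring in the same child. If they occur independently, the overlap counts once. For b = 20%: (0.19 − 0.10 × 0.09) / (0.14 − 0.05 × 0.09) = 0.181 / 0.1355 = 1.34. The extra loss is small beside the dilution.

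**Do the planned safeguards remove it?**
- *Weighting (5.9.1.1).* It balances the groups. The illustration is already balanced, and the dilution is still there.
- *SE sub-tables (5.9.1.2).* Among SE children alone the background is larger, so dilution is greater: b = 20% gives (0.10 + 0.20) / (0.05 + 0.20) = 0.30 / 0.25 = 1.20. SE children also stay in the main results.
- *Excluding pre-existing events (5.9.1.4).* The list behind it has no nervous-system item, so as written it does not act on this outcome.
- *Requiring a related medication or procedure (5.9.1.4).* This asks for confirmation that the event was treated. It does not ask whether a seizure or sedation explains it.
- *Censoring when another AED is added (5.3.3).* This shortens follow-up for some children whose treatment escalates. The AED list in Appendix 1 includes no anaesthetic, midazolam or lorazepam, so sedation need not end follow-up.

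**The case against.** **Table 3 is a candidate list.** Section 5.5.5 says the concepts will be reviewed and case definitions developed with clinicians, and such detail often sits in an analysis plan. This stands in part: the clinicians may deal with the issue. But the protocol itself fixes the components, the first-occurrence rule, the list of sensitivity analyses and the pre-existing list, and none of these mentions states explained by a seizure or sedation.

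**SNOMED-CT concepts can be combined, so an uncaused code does not show that separation fails.** True. But section 5.4.1 states a capability, with a chronic cardiac example. It gives no rule for the seizure disorder itself.

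**Each component has its own rate ratio (5.5.2), and results are stratified by indication (5.9).** Both help. A non-SE stratum would show less dilution, although children treated for other seizures can also be post-ictal. The separate ratios do not give the class-level ratio without the two components, because a child's first event decides what the class counts.

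**The absolute difference is unaffected.** Correct in the balanced case: 0.19 − 0.14 = 0.05, the same as 0.10 − 0.05. But the protocol's comparative measure is the rate ratio.

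**Stronger readings.** A reader might infer that disease course is being attributed to the drug. The documents do not support that: events are all-cause (section 7.1), and section 7.4 says causal linkage for an individual is generally not possible. A reader might also infer that the SE imbalance expected in section 5.1 makes a false excess at high dose in the planned estimate. That would be confounding in a crude ratio, and the planned estimate is weighted on diagnosed conditions, prior seizures and earlier AED or benzodiazepine use. Nor is the direction of a crude ratio settled. With SE at 60% against 30%, b = 20% and a true 2.0, it is (0.10 + 0.12) / (0.05 + 0.06) = 2.0.

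**Conclusion.** The point holds as one of dilution and visibility, and it should be fixed. The primary nervous-system rate ratio mixes events that the dose could cause with states that the treated condition and its management can also cause, and no planned analysis shows the class without them. With SE balanced, a true ratio of 2.0 would appear as about 1.7 to 1.4 on the inputs assumed here, and closer to 1 if disease course makes up more of the comparator events. The size rests on event rates that the protocol does not give. The premise that seizures and sedation produce these states is general clinical knowledge, not a statement in the protocol.

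The all-cause definition is not wrong in itself and should remain the main analysis. A reader might conclude that seizure-day records should simply be excluded from it. That would be unsafe, because the exclusion removes more events from the group with more SE. Taking SE at 60% against 30%, no dose effect, and every event in SE children removed, the crude ratio becomes (0.05 × 0.40) / (0.05 × 0.70) = 0.57, a false protective signal. Section 5.9.4 also expects most events within 24 hours of dosing, which may often be the seizure day.

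**What to change.** Leave the main analysis as it is and make three additions.

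1. **Sections 5.5.5 and 5.9.1.4:** report the nervous-system rate ratio with loss of consciousness and somnolence removed, beside the full outcome. Recompute each child's first event and time at risk from the remaining components.
2. **Section 5.9.1.4:** add a sensitivity analysis that does not count loss of consciousness, somnolence or syncope on a day with a recorded seizure or SE, or with a sedative or anaesthetic administration, where dates in the common data model allow. Report it with the same weighting and with the number of events removed in each group. Table 4 says final diagnoses are recorded per encounter, so the text should say what happens when a day cannot be assigned.
3. **Sections 5.5.3 and 5.9.1.1:** add nervous-system conditions to the pre-existing events, so that the exclusion analysis in section 5.9.1.4 covers them. Define these as prior records of the outcome's own components, not the seizure disorder itself; otherwise the exclusion would remove most of the cohort.

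**Cost.** A little more programming on diagnosis and medication data that the common data model already holds. The restricted analysis loses some drug-caused sedation, possibly unequally between groups, so it must not replace the main analysis.

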### **5.5.2 Secondary outcome measure**

The secondary variables that will be evaluated in this study include:

- Incidence rate and incidence rate ratio of atrioventricular block
- incidence rate and incidence rate ratio of atrioventricular block complete
- incidence rate and incidence rate ratio of atrioventricular block first degree
- incidence rate and incidence rate ratio of atrioventricular block second degree
- incidence rate and incidence rate ratio of arrhythmia
- incidence rate and incidence rate ratio of bradyarrhythmia
- incidence rate and incidence rate ratio of bradycardia
- incidence rate and incidence rate ratio of cardiac fibrillation
- incidence rate and incidence rate ratio of cardiac flutter
- incidence rate and incidence rate ratio of tachyarrhythmia
- incidence rate and incidence rate ratio of atrial fibrillation
- incidence rate and incidence rate ratio of atrial flutter
- incidence rate and incidence rate ratio of cardiac arrest
- incidence rate and incidence rate ratio of torsade de pointes
- incidence rate and incidence rate ratio of ventricular arrhythmia
- incidence rate and incidence rate ratio of ventricular fibrillation
- incidence rate and incidence rate ratio of ventricular tachyarrhythmia
- incidence rate and incidence rate ratio of palpitations
- incidence rate and incidence rate ratio of chest pain
- incidence rate and incidence rate ratio of gait disturbances
- incidence rate and incidence rate ratio of injection site discomfort
- incidence rate and incidence rate ratio of injection site erythema
- incidence rate and incidence rate ratio of injection site irritation
- incidence rate and incidence rate ratio of injection site pain
- incidence rate and incidence rate ratio of stevens-johnson syndrome
- incidence rate and incidence rate ratio of toxic epidermal necrolysis
- incidence rate and incidence rate ratio of angioedema
- incidence rate and incidence rate ratio of urticaria

- incidence rate and incidence rate ratio of pruritus
- incidence rate and incidence rate ratio of rash
- incidence rate and incidence rate ratio of dizziness
- incidence rate and incidence rate ratio of somnolence
- incidence rate and incidence rate ratio of paresthesias
- incidence rate and incidence rate ratio of loss of consciousness
- incidence rate and incidence rate ratio of syncope
- incidence rate and incidence rate ratio of appetite disorder
- incidence rate and incidence rate ratio of decreased appetite

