  - Cardiac flutter
  - Tachyarrhythmia
  - Atrial fibrillation
  - Atrial flutter
  - Cardiac arrest

- 
- Torsade de pointes
  - Ventricular arrhythmia
  - Ventricular fibrillation
  - Ventricular tachyarrhythmia
  - Palpitations
  - Skin and subcutaneous tissue disorders
    - Stevens-Johnson syndrome
    - Toxic epidermal necrolysis
    - Angioedema
    - Urticaria
    - Pruritus
    - Rash
  - Nervous system disorders
    - Dizziness
    - Somnolence
    - Paresthesias
    - Loss of consciousness
    - Syncope
  - Metabolism and nutrition disorders
    - Appetite disorder
    - Decreased appetite
    - Diet refusal
    - Hypophagia
    - Food aversion
  - General disorders and administration site conditions
    - Chest pain
    - Gait disturbances
  - Injury, poisoning and procedural complication
    - Injection site discomfort
    - Injection site erythema
    - Injection site irritation
    - Injection site pain

Table 3 SNOMED-CT concepts for the study	
Study outcome	SNOMED code
Cardiac Disorders	
Atrioventricular block	SCTID: 233917008
Atrioventricular block complete	SCTID: 27885002
Atrioventricular block first degree	SCTID: 270492004
Atrioventricular block second degree	SCTID: 195042002
Cardiac Arrhythmia (disorder)	SCTID: 698247007
Nodal rhythm disorder (disorder)	SCTID: 71792006
Atrial arrhythmia (disorder)	SCTID: 17366009
Cardiac arrhythmia (disorder)	SCTID: 698247007
Atrio-ventricular node arrhythmia (disorder)	SCTID: 88412007
Neonatal dysrhythmia (disorder)	SCTID: 276513001
Electrocardiogram: sinus arrhythmia (finding)	SCTID: 427393009
Ventricular arrhythmia (disorder)	SCTID: 44103008
Premature beats (disorder)	SCTID: 29717002
Electrocardiographic ventricular arrhythmia (finding)	SCTID: 164893009
Supraventricular arrhythmia (disorder)	SCTID: 72654001
Electrocardiographic supraventricular arrhythmia (finding)	SCTID: 164887001
Bradyarrhythmia	SCTID: 421869004
Supraventricular bradyarrhythmia (disorder)	SCTID: 762534000
Bradycardia	
Electrocardiogram: bradycardia (finding)	SCTID: 426627000
Bradycardia (finding)	SCTID: 48867003
Cardiac fibrillation (disorder)	SCTID: 40593004
Ventricular fibrillation (disorder)	SCTID: 71908006
Atrial fibrillation (disorder)	SCTID: 49436004
Rapid atrial fibrillation (disorder)	SCTID: 314208002
Electrocardiographic atrial fibrillation (finding)	SCTID: 164889003

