Paraplegic gait (finding)	SCTID: 250035005
On examination - gait spastic (finding)	SCTID: 163685000
On examination - limping gait (finding)	SCTID: 163691003
Investigations	
ECG PR Prolonged	
Electrocardiogram: partial atrioventricular block - long PR (finding)	SCTID: 164902006
Prolonged PR interval (finding)	SCTID: 164947007
Injury, poisoning and procedural complications	
Injection site discomfort	
Injection site burning (disorder)	SCTID: 95389008
Injection site reaction (disorder)	SCTID: 95377006
Injection site disorder (disorder)	SCTID: 95376002

Table 3 SNOMED-CT concepts for the study	
Study outcome	SNOMED code
Injection site dermatitis (disorder)	SCTID: 95393002
Injection site urticaria (disorder)	SCTID: 95394008
Injection site edema (disorder)	SCTID: 95392007
Swelling at injection site (disorder)	SCTID: 213340005
Injection site inflammation (disorder)	SCTID: 95391000
Injection site induration (disorder)	SCTID: 95402002
Induration at injection site (disorder)	SCTID: 213337005
Injection site hypersensitivity (disorder)	SCTID: 95378001
Injection site cyst (disorder)	SCTID: 95396005
Injection site mass (disorder)	SCTID: 95395009
Injection site ulcer (disorder)	SCTID: 95400005
Injection site abscess (disorder)	SCTID: 95382004
Injection site atrophy (disorder)	SCTID: 95404001
Injection site necrosis (disorder)	SCTID: 95397001
Injection site fibrosis (disorder)	SCTID: 95403007
Injection site bruising (disorder)	SCTID: 95401009
Injection site infection (disorder)	SCTID: 95381006
Injection site granuloma (morphologic abnormality)	SCTID: 24389009
Injection site thrombosis (disorder)	SCTID: 95386001
Injection site hemorrhage (disorder)	SCTID: 95385002
Injection site paresthesia (disorder)	SCTID: 95399003
Injection site nerve damage (disorder)	SCTID: 95390004
Injection site malabsorption (disorder)	SCTID: 95387005
Injection site extravasation (disorder)	SCTID: 95384003
On examination - Injection sites abnormal (disorder)	SCTID: 308092004
Injection site sterile abscess (disorder)	SCTID: 95383009
Injection site pigmentation change (disorder)	SCTID: 95380007
Application AND/OR injection site disorder	SCTID: 95363008
Application site rash (disorder)	SCTID: 95371007
Injection site pain (disorder)	SCTID: 95388000
Erythema at injection site (disorder)	SCTID: 213338000
Injection site irritation (disorder)	SCTID: 95379009
Injection site erythema	

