### 7.4 Reporting obligations

This study uses existing health care databases, in which it is generally not possible to link (i.e., identify a potential causal relationship between) a particular product and medical event for any individual.

This retrospective study (secondary data collection study) is characterized by the secondary use of data previously collected from consumers or healthcare professionals for other purposes. We cannot know if ADR/AEs has been reported previously. Further, initial reporter will not be identifiable (i.e. the 4 elements (compound, AE, Patient, reporter) for a valid Individual Safety Case Report (ICSR) will not be fulfilled.

In addition, this study protocol requires human review of patient-level unstructured data; unstructured data refer to verbatim medical data, including text-based descriptions and visual depictions of medical information, such as medical records, images of physician notes, neurological scans, X-rays, or narrative fields in a database. The reviewer is obligated to report adverse events (AE) with explicit attribution to "Vimpat" that appears in the reviewed information (defined per the patient population and study period specified in the protocol). Explicit attribution is not inferred by a temporal relationship between drug administration and an AE, but must be based on a definite, explicit statement of causality by the original healthcare provider linking drug administration to the AE.

The requirements for reporting safety events on the non-interventional study (NIS) adverse event Report Form to UCB Safety are as follows:

- All serious and non-serious AEs with explicit attribution to "Vimpat" that appear in the reviewed information must be recorded on the chart abstraction form and reported, within 24 hours of awareness, to UCB Safety using the NIS AE Report Form.
- In this study scenarios involving drug exposure that include Vimpat use during pregnancy, during breast feeding, medication error, overdose, misuse, extravasation associated with the use

of “Vimpat” must be reported, within 24 hours of awareness, to UCB Safety using the NIS AE Report Form.

For these safety events with an explicit attribution to or associated with use of, respectively, “Vimpat”, the data captured in the medical record will constitute all clinical information known regarding these AEs. No follow-up on related AEs will be conducted.

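### As coded in Table 3, the secondary outcome Injection site discomfort contains every injection-site code in the table, serious local injury included, and so duplicates the primary Injury outcome

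*Protocol*

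**What the plan says.** Section 5.5.1 makes one of the primary variables "The incidence rate and incidence rate ratio of injury, poisoning and procedural complications (selected PTs as described in Section 5.5.5". Section 5.5.5 then lists four specific events under "Injury, poisoning and procedural complication": injection site discomfort, erythema, irritation and pain. Section 5.5.2 gives each its own secondary result, among them the "incidence rate and incidence rate ratio of injection site discomfort".

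Table 3 assigns the codes. The discomfort sub-heading holds a long list that includes "Injection site necrosis (disorder", "Injection site extravasation (disorder" and "Injection site nerve damage (disorder". The erythema, irritation and pain sub-headings hold one code each.

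Section 5.9.1.2 counts only the first occurrence of an event, stops a patient's time at risk there, and asks for a rate and confidence interval for every subcategory. Section 5.5.5 also says that the Table 3 concepts will be reviewed and that case definitions will be developed with clinicians.

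**The concern.** A subcategory rate is useful only if it shows something that the category total does not. Here the subcategory called discomfort appears to be the whole category, so its rate ratio would repeat the primary one.

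The label is the larger problem. For an intravenous product, local tissue injury is the serious part of this outcome. The protocol recognises the difference elsewhere: section 5.9.4 treats injection site irritation and pain as examples of less severe events, and section 7.4 makes "medication error, overdose, misuse, extravasation associated with the use" of the product reportable within 24 hours. Yet at the level of specific events, Table 3 places extravasation and necrosis with burning and swelling under a name that suggests a minor complaint. A dose-related excess of tissue injury would be averaged with the minor reactions, and no row would show it.

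**Working it through.** **Inputs.** The SNOMED codes under the four Injury sub-headings of Table 3, the outcome definitions in sections 5.5.1, 5.5.2 and 5.5.5, and the counting rule in section 5.9.1.2. The plan states no figure of its own to reproduce.

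**Step 1: compare the code lists.**

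| Sub-heading | Codes | Also in the discomfort list |
|---|---|---|
| Discomfort | 35, all distinct | – |
| Erythema | 1 (213338000) | yes |
| Irritation | 1 (95379009) | yes |
| Pain | 1 (95388000) | yes |

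The union of the four lists has 35 codes and equals the discomfort list. No code of the Injury category lies outside it. The two related codes that Table 3 also places elsewhere, injection site paresthesia (95399003) and application site rash (95371007), are in the discomfort list too.

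Lost layout in the extracted text does not explain this. The erythema, irritation and pain codes appear inside the discomfort block and again under their own sub-headings.

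**Step 2: consequence for the estimates.** With the same codes, a patient's first discomfort event is the same record, on the same day, as the first Injury event. Event counts, time at risk, rates and rate ratios are then equal.

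**Step 3: consequence of counting first events only.** Take a child coded with burning on day 1 and necrosis on day 3. The child contributes one event, and time at risk stops on day 1. The necrosis is counted neither under discomfort nor under Injury, and Table 3 lists it nowhere else.

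**Step 4: dilution.** Let p be the share of tissue injury among comparator-group events. Suppose that tissue injury is three times as frequent in the high-dose group and all other local events are unchanged. If events are rare enough for rates to add approximately,

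IRR = (1 − p) × 1 + p × 3 = 1 + 2p.

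| Assumed p | Calculation | Combined IRR |
|---|---|---|
| 5% | 0.95 + 0.15 | 1.1 |
| 10% | 0.90 + 0.30 | 1.2 |
| 20% | 0.80 + 0.60 | 1.4 |
| 50% | 0.50 + 1.50 | 2.0 |

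Both the threefold excess and the values of p are assumptions; the protocol gives no event frequencies.

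**Step 5: would removing the duplicates be enough?** Taking out the three codes that have their own heading leaves 35 − 3 = 32. These still include necrosis, ulcer, thrombosis, nerve damage and extravasation, so the label problem remains.

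**The case against.** The strongest reply is that Table 3 is not the final definition. Section 5.5.5 foresees review of the concepts and algorithms developed with clinicians, section 5.1 allows procedure and medication codes to be added, and chart review may find further cases. Section 5.4.1 leaves the level of final reporting to be agreed with the sponsor's safety physicians. This stands as a limit: the identity holds for the printed code lists, and a later case definition could separate the two outcomes. It does not remove the point, because none of these sections states a narrower definition of discomfort. The outcome-definition sensitivity analysis in section 5.9.1.4 adds a related medication or procedure code and does not split the list.

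A reader might infer that serious local injury disappears from the study. The documents do not support that. When it is a patient's first local event it stays in the primary Injury total, and section 7.4 requires extravasation found in a reviewed chart to be reported as an individual case. That is a partial safeguard, but it gives no rate by dose group.

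A reader might also infer that any overlap between outcomes is an error, and point to Hypophagia, defined by "Decrease in appetite (finding) Non-organic loss of appetite (disorder" and so lying inside Appetite disorder. The documents do not support that either. Nested terms are common in Table 3; fibrillation and severe cutaneous reactions are built the same way. The analyses are described as rates and rate ratios with confidence intervals, and no significance threshold is stated that repeated counting could breach. The injection-site case differs because one specific term takes in the whole category and its name does not describe its most serious members.

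**Conclusion.** The point holds for the code-based definitions as printed. All 35 injection-site codes in the Injury block fall under discomfort, so that secondary outcome adds nothing to the primary one, and serious local injury has no other specific-event label. Under the first-event rule, a serious event after a minor one is not counted at all.

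The overlap is exact. The loss of signal cannot be fixed from the documents: under the assumed threefold excess, the combined rate ratio runs from about 1.1 to 2.0 as the tissue-injury share goes from 5% to 50%. The statement about completeness covers the codes in Table 3, not SNOMED-CT as a whole, and the concept review in section 5.5.5 could still change the position.

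**What to change.** Make the change at the concept review that section 5.5.5 already foresees.

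- Limit Injection site discomfort to minor local-reaction codes not already used for pain, erythema or irritation.
- Add one secondary row for injection site tissue injury, for example extravasation, necrosis, ulcer, thrombosis and nerve damage. Report counts and rates, with a rate ratio where events allow. Count the first event within this row, so that an earlier minor reaction does not hide it.
- Settle with the clinicians the exact membership of the row and where the non-specific, abscess and infection codes belong.
- Keep the full list of 35 codes for the primary Injury outcome, and say so explicitly, so that narrowing discomfort does not narrow the primary outcome.
- Align the event lists in sections 4, 5.5.2 and 5.5.5.

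No new data are needed, since every code is already in Table 3. The cost is an amendment to the protocol lists, which section 11.4 sends to the sponsor, PEDSnet, the IRB/IEC and the FDA if it is judged significant. Section 5.9.3 expects several hundred patients and section 5.3.3 censors at discharge, so the new row will probably hold few events and any rate ratio will be imprecise. The counts by dose group would still be informative. The primary rate ratio stays diluted as before; the new row is what makes tissue injury visible.
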